Description of Sites/Facilities Enrolling Participants:	All study recruitment and screening will occur at the SENTA Clinic in San Diego, CA, USA; a tertiary referral center which focuses on diseases of the head, neck, brain and spine. All EMG testing procedures will be performed in this clinic under the supervision of an expert otolaryngologist who will obtain the EMG tracings. In-Laboratory polysomnogram (PSG) studies, if required, will be performed at AmeriSleep Diagnostics in San Diego, CA, USA; a comprehensive and ACHC accredited sleep diagnostic facility.
Description of Study Intervention:	Medical device for use as novel diagnostic modality.
	Examination of the electromyographic signal from oropharyngeal muscles obtained using an investigational TM-EMG sensor attached to a rigid probe and a very fine concentric needle electrode (Ambu Neuroline 25 mm x 30G).
Study Duration:	Six months
Participant Duration:	 60 minutes for in-office screening exam. 60 minutes for in-office EMG exam. Healthy participants: One overnight stay for In-Laboratory Polysomnogram (PSG).

STUDY BACKGROUND AND RATIONALE

Electromyography (EMG) is the electrophysiological examination of muscle used for the diagnosis of suspected neuromuscular (NM) disorders such as myopathies, neuropathies, neuronopathies and neuromuscular junction disorders. ¹ Routine needle electromyography studies (NEMG) are mainly restricted to skeletal limb muscles, which are easily accessible, and are not performed routinely on less accessible muscles, such as striated muscles of the oropharynx. This limits the evaluation of neuromuscular involvement in disorders involving muscles of the oropharynx such as obstructive sleep apnea (OSA) and neurogenic oropharyngeal dysphagia. Surface EMG (SEMG) is a non-invasive EMG method that assesses muscle function by recording muscle activity from one or more electrodes placed on the surface of the skin above the muscle or muscles to be examined but lacks the signal quality to provide diagnostic information on individual motor unit morphology and recruitment. ^{2,3}

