- Must be able pause use of anticoagulation, NSAID and multi-vitamins for appropriate period prior to study test. Timeline and safety to be determined by principal investigator.
- A cohort of participants with documented neurological disorders involving upper airway striated muscles including ALS and muscular dystrophy with the presence of bulbar symptoms.
- A cohort of participants diagnosed with moderate to severe OSA on in-lab PSG, including the following criteria:
 - AHI > 25 made up of primarily of obstructive apneas and hypopneas.
 - Nadir Sa02 < 85%
 - Untreated
- A cohort of healthy participants that meet the following criteria
 - o Normal craniofacial anatomy
 - AHI ≤ 2
 - Epworth score ≤ 10
 - Stop-Bang score ≤ 2
 - BMI < 30

Exclusion Criteria

- Allergy to topical anesthetic agent.
- Heavy alcohol use defined as 4 or more alcoholic drinks on the same occasion on 5 or more days in the past month.
- Any type of smoking with 10 days prior testing.
- The presence of any underlying medical, surgical or psychiatric disorder that would preclude participation in the study as determined study principle investigators.

- Prior radiation to the oral cavity.
- Craniofacial anatomical disorders.

Interventions (Diagnostic Procedure)

EMG Testing Procedure

Study participants will be seen by [name] in an outpatient otolaryngology clinic in San Diego, California (SENTA Clinic). Drs. [name] and [name] will serve as consulting physicians. All participants will be evaluated and selected as study candidates based on inclusion/exclusion criteria.

Baseline data obtained will include participant demographic information, a comprehensive history including HPI, medications, past medical history, allergies, family history, social history—including smoking and alcohol consumption, STOP-Bang, and Epworth sleepiness scale. A comprehensive physical examination will be performed. The data will be documented using Cerner Ambulatory Electronic Health Record. Once a candidate is selected for the trial, they will be presented with the risks and benefits of this study. This will be discussed with each participant prior to written consent being obtained. Risks include induction of a gag reflex and/or feeling of nausea, minor irritation or bleeding at the testing site, mild allergic reactions to the topical anesthetic or to the probe tip itself, infection at the needle insertion site. All reactions, if any, are expected to be minor.

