Standard ENT examining room equipment and supplies will be available as part of the study.

The participant will be positioned in a powered reclining and elevating otolaryngology examination chair. The testing physician will stand to the left of the sitting participant, and the participant will be positioned at the appropriate height, head supported in a headrest, to allow the physician to adequately visualize the soft palate anatomy. The physician will use a headlight to illuminate the oral airway. Photographs of the participant and the participant's soft palate/tongue/dentition and oral airway will be taken, and anatomic findings documented. Participant's blood pressure, heart rate, and respiratory rate will be recorded prior to the start of testing.

The skin of the cheek on the zygomatic arch will be prepared and cleaned with an alcohol swab to optimize skin contact with the ground electrode. The investigational TM-EMG probe device is hooked up to the EMG system.

The participant will open his or her mouth adequately to allow for visualization of the soft palate musculature by the physician. For participants in which the palatopharyngeus/ palatoglossus or musculus uvulae are poorly seen, gentle tongue depression will be used to better visualize the anatomy.

Topical 20% Benzocaine will be applied to the mucosal surfaces overlying the muscles to be examined using the TM-EMG probe prior to the start of testing. With the participant's mouth open and in neutral position, the TM-EMG probe is positioned on the mucosal surface correlating to the expected midpoint of the palatoglossus by the co-investigator. Free run EMG recording of the palatoglossus will be obtained. Once an optimal EMG tracing is obtained the probe will be released off the mucosal surface. The same procedure is repeated on the contralateral palatoglossus.

The same protocol will be used to test the genioglossus. The TM-EMG probe is placed on the mucosa of the genioglossus until an optimal EMG tracing is obtained. The same procedure is repeated on the contralateral genioglossus.

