The principal investigator will then take his turn at assessing the same muscles. The palatoglossus will be examined in the same location using the same TM-EMG probe. Once an optimal EMG recording is obtained, the TM-EMG probe will be released off the mucosal surface and a very fine concentric needle electrode (Ambu Neuroline 25 mm x 30G) will be placed into the palatoglossus using the procedure as described below. Needle insertion will be done in a straight line through the mucosal membrane into the midpoint of the muscle at the desired depth. 1-3 needle insertions will be used to obtain a diagnostic-quality EMG tracing from each muscle. The needle is placed in the same location tested by the TM-EMG probe. Once both tracings are recorded, the contralateral palatoglossus will be tested via both TM-EMG and NEMG. The principal investigator will then obtain bilateral genioglossus EMG using the same protocol that was used for the palatoglossus.

The principal investigator will also obtain EMG data from both left and right palatopharyngeus using the TM-EMG probe and associated protocol. However, due to anticipated difficulty with gag reflex associated with the palatopharyngeus, NEMG will not be used at this site, and testing of this muscle will only be performed by the principal investigator. In total, 6 muscles locations will be tested via TM-EMG, and 4 muscle locations by NEMG.

The free-run EMG tracing for both TM-EMG and NEMG will be displayed on an oscilloscope and heard through an audio-amplifier. All EMG recordings will be made using standard gain and sweep speed settings. Waveforms for both TM-EMG and NEMG tests will be recorded on a Cadwell Sierra Summit EMG system.

We anticipate the recording time per muscle will be approximately 10 seconds. If participant exhibits intolerance during an individual muscle test, that particular muscle test will be discontinued.

The participant will be examined at the conclusion of the EMG procedures for excessive bleeding or swelling. The participant will have blood pressure, heart rate, and respiratory rate checked for stability immediately upon completion of testing and prior to discharge. The participant will be given written instructions on how to contact the research staff should any adverse events arise, such as a sore throat, fever, testing site irritation or any other study

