related concerns. The research staff will contact the participant 1 day and 7 days after completion of the EMG test to document any adverse events the participant may have had following the testing. Responses will be documented in the EMR and serious adverse events will be reported to the study sponsor and IRB within 24 hours. Adverse events which occur more than 5 days after the EMG test will not be considered related to the study intervention, unless the investigator suspects a potential link.

Sleep Study

All healthy study participants selected for the study will be required to complete an overnight stay for an in-laboratory Polysomnogram ("PSG").

Study Endpoints

Primary Endpoint

Proof of diagnostic consistency using both the TM-EMG sensor and NEMG in neuromuscular disorders of the oropharyngeal muscles.

TM-EMG and NEMG data will be analyzed offline upon completion of testing by [name]. Analysis will include the presence of spontaneous activity (fibrillation potentials and positive sharp waves), MUP morphology (number phases, duration and amplitude) and recruitment pattern. MUP morphology will be analyzed manually. Each recording will be labeled as a normal or abnormal study. Abnormal studies will be classified into active or chronic neurogenic changes or myopathic changes.

Secondary Endpoint

Proof that participants with known OSA exhibit EMG findings different from healthy participants and that these findings can be detected using both the needle electrode and the transmembrane sensor.

Analysis results will be compared between the healthy cohort and the neurologic disorders cohort; and between the healthy cohort and the OSA cohort.

Sample Size Calculation

Given that this is a novel EMG testing technique, a formal sample size calculation was not performed. The sample size chosen for this study was based on what would be reasonably feasible given constraints in areas such as funding and recruiting. The results from this pilot study will enable design of a larger, multi-site study adequately powered to show the diagnostic usefulness of TM-EMG.

Statistical Methods

All data will be examined to determine if there are any missing or non-plausible values, and these will be removed. Summary statistics will be calculated, including means or medians, minimums and maximums, standard deviations, and interquartile ranges.

The distribution of EMG findings in OSA will be presented as descriptive statistics.

ADVERSE EVENT MONITORING

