Documented above under Interventions.

STUDY DISCONTINUATION

Participants will be withdrawn from the study if they withdraw consent or if the study physician determines that there is a safety risk associated with their participation. If a participant exhibits intolerance during an individual muscle test, that particular muscle test will be discontinued.

ANCILLARY OR POST-TRIAL CARE

Following the trial, each participant will return to the clinical care of their original physician. We will also assume responsibility for any adverse effects or harms caused by the intervention.

ETHICS AND DISSEMINATION

Research Ethics Approval, Protocol Amendments, and Consent

Participants who are eligible for study participation will be approached by the research assistants, to avoid any coercion on the part of the investigators. Consent will be obtained in writing, with the risks and potential benefits of the study clearly explained in basic language in the consent form. The participant will be allowed ample time to review the consent form prior to signing; and if the participant wishes to discuss the study with family members prior to going forward, they may take the consent form home. The research assistants will be available to answer any questions about the study; and if the research assistants are unable to answer the question, this will be addressed by the study investigator. All participants will be re-assured that at any point during the study, they may withdraw consent and end their participation in the study. If consent is withdrawn, all data collected to that point remains as part of the study, however, will be de-identified.

The study will be conducted in accordance with International Conference on Harmonisation Good Clinical Practice (ICH GCP), applicable United States (US) Code of Federal Regulations

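### No scheduled adverse-event enquiry covers the pre-test pause in anticoagulants, NSAIDs and multivitamins that participants must be able to make

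*Combined protocol and SAP*

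**What the plan says.** The combined protocol and SAP makes it an inclusion criterion that participants can "pause use of anticoagulation, NSAID and multi-vitamins for appropriate period prior to study test. Timeline and safety to be determined by principal investigator" (Eligibility Criteria, Inclusion Criteria). No length of pause is fixed and no restart time is given.

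Adverse-event collection is described in Interventions (Diagnostic Procedure), EMG Testing Procedure. Research staff "will contact the participant 1 day and 7 days after completion of the EMG test", and the purpose is "to document any adverse events the participant may have had following the testing". In addition, "serious adverse events will be reported to the study sponsor and IRB within 24 hours". The section headed Adverse Event Monitoring adds nothing of its own; its content is "Documented above under Interventions".

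On the test day, the only scheduled safety step before testing is that "blood pressure, heart rate, and respiratory rate will be recorded prior to the start of testing". After testing there is an examination for bleeding and swelling, and the vital signs are repeated.

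Study Discontinuation allows withdrawal when the study physician sees a safety risk.

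**The concern.** Stopping a medicine carries its own risk, above all for an anticoagulant. Here the reason for stopping would be a research procedure, and the stopping happens before that procedure. The adverse-event schedule, however, starts only when the procedure is finished. Followed as written, it does not ask about a period of risk that the study creates.

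What is at stake is participant safety reporting. An event that begins while a medicine is withheld for the study, and that the participant does not volunteer, would not be asked about and so might never reach the sponsor or the IRB. The primary and secondary endpoints are diagnostic EMG comparisons and do not depend on this.

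**Working it through.** No arithmetic decides the point. The check sets the pause, which runs from an unstated day up to the test, against each safety step in the protocol.

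| Step | Where described | When | Asks about events during the pause? |
|---|---|---|---|
| Baseline history and examination | EMG Testing Procedure | Described before selection and consent | No |
| Overnight sleep study (healthy cohort only) | Sleep Study | Timing relative to the pause not stated | No adverse-event question described |
| Vital signs: blood pressure, heart rate, respiratory rate | EMG Testing Procedure | Just before testing | No: 3 measurements, 0 adverse-event questions |
| Examination for bleeding and swelling; repeat vital signs | EMG Testing Procedure | After testing | No |
| Staff contact, day 1 | EMG Testing Procedure | 1 day after EMG completion | No: scope is events after testing |
| Staff contact, day 7 | EMG Testing Procedure | 7 days after EMG completion | No: same scope |

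Three steps of reasoning follow.

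1. **Scheduled enquiries.** There are 2, and both the timing and the stated scope of each lie after the test. The number covering onset before the test is 0 of 2. If a pause ran on past the test, later events would fall within these contacts, but the criterion describes the pause as preceding the test.

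2. **Baseline history.** It is described before a candidate is selected and consents, so it would normally precede any pause ordered by the study. The Study Summary lists "60 minutes for in-office screening exam" separately from the 60-minute EMG exam. The interval between the two is not given, so this step rests on the order of the narrative rather than on an explicit statement.

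3. **Number who could be affected.** Planned participants are 10 (neuromuscular disorders) + 5 (OSA) + 8 (healthy) = 23. That is only an upper limit. The criterion requires the ability to pause, not that anyone is taking one of these medicines. The number who would pause, the length of the pause and the risk of an event are not in the documents.

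The 0 of 2 is a count of coverage. It does not measure how often an event would be missed.

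**The case against.** The strongest reply is that the pause is not unsupervised. The same criterion gives its timing and safety to the principal investigator. That investigator also performs the needle EMG, and so meets the participant face to face on the day. Participants can be excluded or withdrawn on safety grounds, and the protocol accepts responsibility for harms caused by the intervention (Ancillary or Post-Trial Care). The 24-hour rule for serious events has no stated start time, so a serious event during the pause that staff learn of would fall under it. On this view a standard prompt is missing, not oversight, and no one is shown to be exposed.

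Most of this stands, and it keeps the point small. It does not close the gap. Judging beforehand that a pause is safe is different from asking afterwards what happened. The reporting and withdrawal rules work only once someone knows of the event. The protocol itself saw a need for two scheduled enquiries after a test whose reactions it expects to be minor. One question about the pause is in keeping with that standard.

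Stronger readings are tempting, and the documents do not support them:

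- **That the pause is made without safety oversight.** The principal investigator's role contradicts this.
- **That participants cannot reach staff before the test.** The one visible mention, "The participant will be given written instructions on how to contact the research staff should any adverse events arise", comes in the end-of-test paragraph, but the consent pages are not in the copy reviewed and may give contact details earlier. No absence is claimed, and no change to the instructions is proposed.
- **That participants whose EMG is cancelled are lost to follow-up.** Both contacts are timed from EMG completion, so read literally neither would be triggered. But the protocol does not describe a cancelled EMG, and this is inference from silence.
- **That a known number of participants is at risk, or that the EMG comparison is biased.** Nothing in the documents gives such a number, and the endpoints are unaffected.

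**Conclusion.** The point holds as a minor gap in safety reporting. The protocol provides for a pause in medication before the test, and neither of its 2 scheduled adverse-event enquiries, nor the pre-test step, asks about events during that pause. Confidence in this reading of the text is high. Its practical consequence cannot be estimated: it depends on how many of the 23 planned participants pause a medicine (anticoagulants mattering most), for how long, and whether they would mention an event unprompted.

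The conclusion assumes that the baseline history precedes the pause, as the order of the text implies, and that no enquiry about the pause is specified on pages not available for review.

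**What to change.** Make two changes to the protocol:

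1. Start the adverse-event recording period at the first dose of any medicine withheld at the study's direction.
2. At the EMG visit, before testing and alongside the vital signs, ask each participant who paused a medicine about any event since the pause began. Record and report what is found under the existing rules.

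Which medicines are paused, and for how long, stays with the principal investigator.

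The cost is protocol wording and at most 1 × 23 = 23 extra questions at a visit that already takes place. No visit or procedure is added.

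Optionally, add one follow-up call to anyone who paused a medicine but whose EMG was then cancelled. The number of such calls is not known from the documents.

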Transmembrane Electromyography (TM-EMG) for the Assessment of Neuromuscular Function in the Oropharynx

Principal Investigator: [name].

Co-Principal Investigator: [name].

Subinvestigator: [name].

Sponsor: Powell Mansfield, Inc. Funded by: Powell Mansfield, Inc.

Version 2

April 4, 2019

STUDY SUMMARY

Study Description:	Transmembrane electromyography (TM-EMG) may be a feasible and
	valid non-invasive EMG technique for detecting neuromuscular (NM)
	impairment. This study will assess whether, in healthy volunteers and
	participants with known obstructive sleep apnea (OSA) and other NM
	diseases involving the oropharynx, the same characteristic motor unit
	potentials obtained on conventional needle EMG (NEMG) can be
	obtained using a TM-EMG sensor. The purpose of this study is to
	demonstrate whether the TM-EMG sensor can provide the
	same diagnostic accuracy as the concentric needle electrode for the
	diagnosis of NM diseases. Having demonstrated diagnostic similarity of
	TM-EMG to NEMG, the secondary aim of this study is to confirm that
	NM disturbance of oropharyngeal striated muscles in participants with
	OSA can be elicited with the TM-EMG sensor.

Objectives: Primary Objective: To validate the TM-EMG sensor as a non-invasive technique for the assessment of neuromuscular function in the oropharynx.

Secondary Objective: To elicit, using the TM-EMG sensor, neuromuscular findings that correlate to OSA in affected participants.

Endpoints: Primary Endpoint: Proof of diagnostic consistency using both the TM-EMG sensor and NEMG in neuromuscular disorders affecting oropharyngeal muscles.

Secondary Endpoint: Proof that participants with known OSA exhibit EMG findings different from healthy participants and that these findings can be detected using both the NEMG and the TM-EMG sensor.

- **Study Population: I**5 total participants with disorders affecting the function of oropharyngeal muscles
 - 10 participants with one of the following neuromuscular disorders:

	 ALS with the presence of bulbar symptoms
	 muscular dystrophy with the presence of bulbar symptoms
	• 5 participants with severe OSA
	8 healthy volunteer participants
Phase:	Pilot

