Although the complications of OSA are well known, the physiological mechanism for upper airway collapse during inspiration and sleep is not clear. Nonetheless, there is substantial physiological, electrophysiological and histological evidence for neuromuscular impairment in the upper airway in participants with OSA, ²⁶ and pharyngeal nerve injury has been proposed as a possible contributory factor in OSA development, ² which might be related to vibratory trauma caused by sleep-disordered breathing. ⁷ Evidence for sensory involvement in participants with OSA includes the finding of abnormal two-point palatal sensory discrimination, ⁸ and disordered thresholds for warmth and cold detection in the oropharyngeal mucosa.⁹ Although the activity of the genioglossus, an upper airway dilator muscle, was found to be significantly greater during wakefulness in OSA, possibly due to a reflex-driven neuromuscular compensation for an anatomically compromised airway, a greater decline was observed during the early and late sleep onset period, suggesting the loss of this reflex. ¹⁰ Evidence for motor nerve fiber loss was shown by needle electromyography (EMG), demonstrating longer duration motor unit potentials (MUP) with larger size index.² Histological evidence for neuromuscular impairment in the upper airways includes frequent focal degeneration of myelinated nerve fibers and axons,⁹ increased number of sensory and motor nerve fibers, indicating peripheral sprouting secondary to neuropathy, ¹¹ abnormal muscle fiber variability with increased amount of connective tissue, and alternation in myosin heavy chain compositions. 12,13

Dysphagia is difficulty swallowing due to structural or functional impairment of the aerodigestive tract. Such impairment may arise from an underlying neurological disorder producing oropharyngeal dysphagia (OPD). Participants with OPD have difficulty initiating swallowing and present with choking, nasal regurgitation or coughing episodes while eating, and drooling due to difficulty managing saliva. In addition, neurogenic OPD may be complicated by aspiration pneumonia, dehydration and malnutrition, increasing the morbidity of the underlying neurological disorder. Participants with symptoms of oropharyngeal dysphagia undergo a VFSE, which in the case of neurogenic OPD, typically reveals impairment of oropharyngeal motor performance and/or laryngeal protection. ¹⁴

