Electrophysiologic examination of muscles can provide diagnostic information as to the underlying process: myopathy, neuropathy, neuronopathy or neuromuscular junction disorders. There are currently two primary types of EMG techniques or methods: intramuscular or needle EMG (NEMG) and surface EMG (SEMG). NEMG involves the insertion of a needle electrode directly into the muscle to be examined and is considered the gold standard for assessing the muscle attributes of neuromuscular diseases. NEMG allows the clinician the ability to provide a precise evaluation of key indicators of neuromuscular function such as

spontaneous activity and motor unit action potential (MUAP) recruitment and morphology. These indices are utilized to: 1) differentiate between primary muscle pathology and muscle dysfunction secondary to nerve injury 2) characterize the nature of the pathology by the assessment of denervation activity which is typically indicative of an active disease process 3) assess re-innervation changes indicating disease chronicity and 4) define the topographical distribution of the neuromuscular disorder. ¹

However, NEMG is invasive and painful. Insertion of the needle damages the pierced tissues causing swelling and bleeding and nociceptor activation causes pain. There is risk of infection, viscus perforation and disease transmission. ³ These drawbacks are especially evident in areas of the body that are sensitive or dangerous places to use a needle such as the mouth/pharynx, eyes, ears, GI tract, urinary system, and myocardium. Consequently, NEMG is not used in these areas routinely in EMG laboratories. In an awake participant, needle electrode placement into oral or pharyngeal muscles is constrained by the gag reflex, insertion pain, procedure fear, local trauma, and bleeding risk. Once inserted, the needle electrode must be optimally positioned to record muscle activity. This requires repositioning of the needle in the muscle which further challenges participant tolerance and compliance.

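### ALS and muscular dystrophy are compared with healthy participants as one cohort, so a pooled mean of motor unit duration or amplitude can hide opposite shifts

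*Combined protocol and SAP*

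**What the plan says.** The Study Summary plans "10 participants with one of the following neuromuscular disorders", naming ALS and muscular dystrophy, both with bulbar symptoms, and "8 healthy volunteer participants". It sets no number per disease. The Inclusion Criteria treat the two diseases as one cohort: "A cohort of participants with documented neurological disorders involving upper airway striated muscles including ALS and muscular dystrophy with the presence of bulbar symptoms".

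Under Study Endpoints, Secondary Endpoint, the between-group plan is: "Analysis results will be compared between the healthy cohort and the neurologic disorders cohort; and between the healthy cohort and the OSA cohort". The Statistical Methods section adds: "Summary statistics will be calculated, including means or medians, minimums and maximums, standard deviations, and interquartile ranges". That sentence names no variable, cohort or diagnosis.

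The Primary Endpoint section lists what is read from each recording. It includes the duration and amplitude of motor unit potentials (MUPs), a normal or abnormal label, and, for abnormal recordings, a neurogenic or myopathic class.

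The Study Background and Rationale places ALS among neurologic disorders and muscular dystrophy among myopathies. It describes needle findings of motor nerve fiber loss in sleep apnea as "demonstrating longer duration motor unit potentials (MUP) with larger size index". It also gives, as the first use of needle EMG, the ability to "differentiate between primary muscle pathology and muscle dysfunction secondary to nerve injury".

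**The concern.** MUP duration and amplitude are signed measures. They can move up or down from the healthy value. If nerve disease moves them up and muscle disease moves them down, averaging over a mixed cohort sets one against the other. Every patient could be clearly abnormal while the cohort mean sits near the healthy mean.

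Two things are at stake. First, the pilot is meant to support the design of a larger study, and a pooled shift near zero with an inflated SD would misinform it. Second, the protocol recruits one muscle disease and one disease it lists as neurologic, and names telling muscle from nerve pathology as a main use of EMG. Its only stated contrast of these patients with healthy participants then merges them.

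**Working it through.** The plan gives no effect size, SD, test, alpha or power, so there is no figure of its own to reproduce. What follows illustrates the size of the effect.

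**From the documents:** 10 neurological participants, any split; 8 healthy.

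**Assumed:** participant-level MUP duration with healthy mean 100% and between-person SD 15%; ALS +30%; dystrophy −30%; two-sided 5% Welch test as yardstick only.

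With k ALS and 10 − k dystrophy participants:

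- Pooled mean shift = [30k − 30(10 − k)]/10.
- Expected pooled sample variance = 15² + (10/9)(k/10)(1 − k/10)(60)².

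At 5:5 the shift is (150 − 150)/10 = 0. The variance is 225 + (10/9)(0.25)(3600) = 1225, so the SD is 35% against 15% in healthy participants. At 7:3 the shift is (210 − 90)/10 = 12%. The variance is 225 + (10/9)(0.21)(3600) = 1065, so the SD is about 33%.

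Detection rates come from simulation with 20,000 replicates:

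| ALS : dystrophy | Pooled mean shift | Pooled detection | Detection by disease (ALS, dystrophy) |
|---|---|---|---|
| 5:5 | 0% | about 0.1% | 86%, 86% |
| 7:3 | +12% | 5% | 94%, 59% |
| 8:2 | +18% | about 27% | not tabulated |
| 9:1 | +24% | 71% | not tabulated |

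Because the assumed shifts are equal and opposite, 3:7 mirrors 7:3.

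**Median.** At 5:5 it also goes to about 0. At 7:3 it shifts by about +22%, against +12% for the mean, so it hides less at uneven splits.

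**Other equal shifts and SDs.** Over shifts of 20% to 40% and SDs of 15% to 20%, pooled detection stays at or below about 6.5% for splits from 7:3 to 3:7. By disease it runs from 23% to nearly 100%. At 8:2 the pooled rate is about 15% to 32%, and at 9:1 it is 29% to 88%.

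**Unequal shifts.** With ALS +30% and dystrophy −15%, a 5:5 split gives a pooled shift of (150 − 75)/10 = 7.5% and detection of 3%, against 86% and 34% by disease. At 7:3 the shift is (210 − 45)/10 = 16.5% and pooled detection is about 27%. At 3:7 it is (90 − 105)/10 = −1.5% and about 1%. Cancellation is then partial, and the worst split moves away from 5:5.

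**Labels.** The abnormal label has no sign, so it cannot cancel. As an illustration, 8 of 10 abnormal against 1 of 8 gives Fisher p = 0.015 whatever the disease split.

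**The case against.** The strongest reply is that the plan already holds a safeguard. Each recording is labeled normal or abnormal, and abnormal ones are classed as neurogenic or myopathic. Neither output cancels, and the second keeps the direction of change. This stands, and it limits the damage. It does not close the gap, because the plan never says that the class will be set against the documented diagnosis. In counts over the merged 10, a dystrophy recording read as neurogenic looks the same as a correct ALS reading.

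Several further points also stand:

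- The plan does not say that means or medians are the measure for the pooled comparison; it compares analysis results in general. They are, however, the natural summaries of duration and amplitude.
- The planned SD, range and interquartile range would hint at mixing, though they would not give each disease's shift.
- The opposite direction of myopathic change is not in the documents.
- No hypothesis test is planned, so the detection rates are a yardstick and not a property of the study.

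A reader might infer that the sensor would look blind to disease. The documents do not support that. Needle and TM-EMG are recorded at the same sites in the same participants, so pooling flattens both devices alike. The primary endpoint is their consistency with each other, not a contrast with healthy participants.

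**Conclusion.** The point holds as a defect in the between-cohort comparison listed under the secondary endpoint. As written, that comparison merges two diseases that the protocol itself places in different classes, fixes no split and plans nothing by diagnosis. Whether real shifts in MUP duration or amplitude are then hidden depends on three assumptions: opposite directions, shifts of similar size, and a split between about 7:3 and 3:7. When these hold, the pooled mean is close to uninformative, while each disease alone could show a clear difference. A reader might take cancellation as certain. It is not: it weakens quickly at 8:2 and 9:1, and does not arise if only one disease is enrolled.

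The primary comparison of TM-EMG with needle EMG is unaffected. In a descriptive pilot this is a change that should be made, not a fatal flaw.

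**What to change.** In the Secondary Endpoint section, replace the single healthy-versus-neurologic comparison of MUP duration and amplitude with two: healthy versus ALS and healthy versus muscular dystrophy, each by device and muscle. In Statistical Methods, add a table of TM-EMG class against needle class (normal, neurogenic, myopathic) within each documented diagnosis, for the muscles tested by both methods. If one summary of all 10 is wanted, use the proportion of participants abnormal in the direction expected for their diagnosis, and state how several recordings are combined into one result per participant.

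No new data are needed, since the diagnosis is documented at entry. The cost is smaller groups and wider intervals. At a common SD of 15%, the standard error of a difference is 15 × √(1/10 + 1/8) = 7.1% for 10 versus 8, and 15 × √(1/5 + 1/8) = 8.6% for 5 versus 8. The 7.1% is reached only if the two diseases shift alike. With the opposite shifts assumed above and a 5:5 split, the pooled standard error is √(1225/10 + 225/8) = 12.3%. If one disease contributes only one or two participants, list their values individually.
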